6.1.5 Methods and Timing for Assessing, Recording, and Analysing Variables

Four visits are scheduled during the course of the clinical investigation as presented below:

Visit#1 (Screening Visit): Day 1-10 to Day 1-7 (Run-in Period)

Visit#2 – D1 (Randomisation Visit): Day 1

Visit#3 – D15: Day 15 (± 1 day)

Visit#4 – D36 (Final Visit): Day 36 (± 3 days) or Premature Discontinuation Visit.

Visits should be performed at the same hour (± 2 hours) in the morning.

6.1.5.1 *Screening Period*

Visit#1: Screening Visit (Day 1-10 to /Day 1-7)

Visit#1 will consist of the following procedures and examinations by the investigator or authorised delegate who will perform the ophthalmologic examination during all the visits and according to the following order in each eye.

By the masked investigator or authorised delegate (according to local requirements, the investigator may delegate tasks to collaborator).

- Information for the patient and signature of the informed consent (can be done before this visit, see Section 13).
- Demography
- History of the dry eye
- Questioning about ocular and systemic medical, and surgical history (other than dry eye)
- Questioning about previous and concomitant ocular and non-ocular treatments
- Urine pregnancy testing (if applicable)
- Measurement of far BCVA*
- Slit lamp examination*
- Verification of inclusion and exclusion criteria
- Status of the patient (start of run-in period or not)
- Run-in treatment dispensation
- Patient diary dispensation.
- The following instructions will be given to the patient:

The next visit must be scheduled within 7 to 10 days later at the same hour, in the morning (\pm 2 hours).

Site staff must remind the patients:

- how to complete the patient diary,
- to bring the patient diary back at Visit #2,
- how to instil Hydrabak® and to respect the posology of 1 drop in each eye, from 3 to 6 times daily,
- that no preservative-free artificial tears (Hydrabak®) must be instilled for at least 6 hours before Visit#2,
- to bring back used preservative-free artificial tears (Hydrabak®) for compliance check at Visit#2.

The run-in period duration will be calculated based on the start and end dates of Hydrabak®. The start and end dates of run-in period will be the start date of Hydrabak® and the end of run-in period will be the end date of Hydrabak®.

*Ophthalmological examinations and assessments MUST be performed by the SAME masked investigator for all the visits and using the same slit lamp.

6.1.5.2 *Treatment Period*

Visit#2: Randomisation Visit (Day 1)

Visit#2 will consist of the following procedures and examinations by the investigator or authorised delegate who will perform the ophthalmologic examination during all the visits and according to the following order in each eye.

By the masked investigator or authorised delegate, the same as the screening visit (according to local requirements, the investigator may delegate tasks to collaborator).

- Questioning about previous and concomitant ocular and non-ocular treatments
- OSDI Questionnaire
- DEAL questionnaire
- Ocular discomfort (VAS)
- Questioning about dry eye related ocular symptoms within the last 48 hours
- Measurement of Far BCVA*
- Tear Sampling for IL6 and IL8 concentration assessment**
- Slit lamp examination* for measuring:
 - Measurement of conjunctival hyperaemia* [REDACTED]
 - [REDACTED] Oxford 0-15 grading scheme* (corneal staining by fluorescein and conjunctival staining by fluorescein with yellow filter),
 - TBUT*
- Schirmer test* (without anaesthesia)
- AE reporting
- Verification of inclusion and exclusion criteria
- Randomisation (IRT system)
- IMD dispensation
- Questioning about Run-in treatment compliance
- Check of the patient diary completion with the patient
- Status of the patient (Screen failure or randomised)

By the unmasked collaborator:

- Incidents reporting

The next visit must be scheduled 15 days after Visit #2 (± 1 day) at the same hour (± 2 hours).

Site staff must remind the patients:

- how to complete the patient diary,
- to not report any information that could lead to unblinding in the diary,
- to not report any information that could lead to unblinding to the masked investigator,
- to bring the patient diary back at Visit #3,
- how to instil IMD and to respect posology of 1 drop in each eye, from 3 to 6 times daily,
- that no IMD must be instilled for at least 2 hours before Visit#3.

*Ophthalmological examinations and assessments MUST be performed by the SAME masked investigator for all the visits and using the same slit lamp.

**It's necessary to wait at least 15 minutes after tear sampling to perform the next ophthalmic assessment.

Visit#3: Day 15 (\pm 1 day)

Visit#3 will consist of the following procedures and examinations by the investigator or authorised delegate who will perform the ophthalmologic examination during all the visits and according to the following order in each eye.

By the masked investigator or authorised delegate (the same as the screening visit) (according to local requirements, the investigator may delegate tasks to collaborator).

- Questioning about previous and concomitant ocular and non-ocular treatments
- OSDI Questionnaire
- DEAL questionnaire
- Ocular discomfort (VAS)
- Questioning about ocular symptoms immediately after drop instillation,
- Questioning about dry eye related ocular symptoms within the last 48 hours
- Assessment of global performance by the patient
- Assessment of the ocular tolerance by the patient
- Measurement of Far BCVA*
- Tear Sampling for IL6 and IL8 concentration assessment**
- Slit lamp examination* for measuring:
 - Measurement of conjunctival hyperaemia* [REDACTED]
 - [REDACTED] Oxford 0-15 grading scheme* (corneal and conjunctival staining by fluorescein with yellow filter)
 - TBUT*
- Schirmer test* (without anaesthesia)
- AE reporting
- Assessment of the ocular tolerance by the investigator
- Assessment of the performance by the investigator
- IMD dispensation
- Questioning about IMD compliance
- Check of the patient diary completion with the patient

*Ophthalmological examinations and assessments MUST be performed by the SAME masked investigator for all the visits and using the same slit lamp.

**It's necessary to wait at least 15 minutes after tear sampling to perform the next ophthalmic assessment.

By the unmasked collaborator:

- Recording the number of returned used and unused IMD in source document (the accountability is expected for the quantity of bottles) and transfer this information to masked investigator for compliance assessment.
- Incidents reporting

The next visit must be scheduled 36 days after Visit #2 (± 3 days) at the same hour (± 2 hours).

Site staff must remind the patients:

- how to complete the patient diary,
- to not report any information that could lead to unblinding in the diary,
- to not report any information that could lead to unblinding to the masked investigator,
- to bring the patient diary back at Visit #4.
- how to instil IMD and to respect the posology of 1 drop in each eye, from 3 to 6 times daily,
- that no IMD must be instilled for at least 2 hours before Visit#4.

Visit#4: Day 36 (± 3 days)

Visit#4 will consist of the following procedures and examinations by the investigator or authorised delegate who will perform the ophthalmologic examination during all the visits and according to the following order in each eye.

By the masked investigator or authorised delegate (the same as the screening visit) (according to local requirements, the investigator may delegate tasks to collaborator).

- Questioning about previous and concomitant ocular and non-ocular treatments
- OSDI Questionnaire
- DEAL questionnaire
- Ocular discomfort (VAS)
- Questioning about ocular symptoms immediately after drop instillation,
- Questioning about dry eye related ocular symptoms within the last 48 hours
- Assessment of global performance by the patient
- Assessment of the ocular tolerance by the patient
- Measurement of far BCVA*
- Tear Sampling for IL6 and IL8 concentration assessment**
- Slit lamp examination* for measuring:
 - Measurement of conjunctival hyperaemia* [REDACTED]
 - [REDACTED] Oxford 0-15 grading scheme* (corneal and conjunctival staining by fluorescein with yellow filter)
 - TBUT*
- Schirmer test* (without anaesthesia)
- Urine pregnancy testing
- AE reporting

*Ophthalmological examinations and assessments MUST be performed by the SAME masked investigator for all the visits and using the same slit lamp.

**It's necessary to wait at least 15 minutes after tear sampling to perform the next ophthalmic assessment.

- Assessment of the ocular tolerance by the investigator
- Assessment of the performance by the investigator
- Questioning about IMD compliance
- Check of the patient diary completion with the patient

By the unmasked collaborator:

- Recording the number of returned used and unused IMD in document source (the accountability is expected for the quantity of bottles) and transfer this information to masked investigator for compliance assessment.
- Incidents reporting

6.1.5.3 Additional/Optional Visit(s) during the clinical investigation

NA

6.1.5.4 Premature Discontinuation Visit during the clinical investigation

A patient who prematurely discontinues from the clinical investigation should have, if possible, a Premature Discontinuation Visit. This last site visit should take place as soon as possible after the patient stops taking IMD. All follow-up procedures and examinations scheduled to be performed at the final visit should be performed at the patient's premature discontinuation visit.

If the patient is tested COVID-19 positive during the course of the clinical investigation, the patient has to inform the investigator. Either the patient may continue the clinical investigation when he/she can follow the CIP requirements safely and in accordance with the national/regional recommendations or the patient may be withdrawn from the clinical investigation.

6.1.5.5 Additional Follow-Up Visit(s) (after the end of the treatment)

NA

6.1.5.6 Adaptive Follow-Up of Patients Prematurely Withdrawn due to an Exceptional Circumstance (e.g. COVID-19 pandemic)

The benefit/risk ratio will be evaluated both by the Sponsor at global level (regulatory requirement) and by the investigator regarding the situation and local regulatory requirements in his/her country/region and in his/her own investigational site.

If the patient withdrew from the investigation due to an exceptional circumstance, and if an onsite visit was not authorised, a premature discontinuation visit by phone is required.

- Premature discontinuation phone call

- Check the IMD compliance with the patient.
- Instruct the subject to stop the IMD and keep used and unused IMD for later return.
- Ensure the continuity of artificial tears medication as per routine clinical practice.
- Collect AE/Serious Adverse Event (SAE), incidents and any changes in concomitant treatments.

- Plan a safety onsite visit 4 weeks later (± 7 days) and ensure that the patient understands all recommendations.
- Record the phone call and all information collected in the patient medical record.

- **Safety Follow-up visit on site**

During the onsite follow-up visit done 4 weeks (± 7 days) after the premature discontinuation phone call, the following procedures are required:

- Ensure that dry eye is well controlled.
- Check the IMD compliance with the patient.
- Record the number of the returned used and unused IMD (by the authorised unmasked delegate).
- Check that the patient had stopped the IMD and takes the new treatment, collect start and end dates of these medications.
- Collect AE/SAE, incidents and any changes in treatments.
- Record the visit and all information collected in the patient medical record.

If a safety onsite visit is still not possible, the follow-up will be done by phone or online video consultation and the patient is asked to return the used and unused investigation products later, when the situation improves or the pickup of the IMD directly from the patient will be organised. The compliance will be checked with the number of the returned used and unused IMD.

6.1.6 Equipment to be used for Assessing the Clinical Investigation Variables and Arrangements for Monitoring Maintenance and Calibration

A slit lamp will be used to measure the total ocular surface staining grade according to [REDACTED] Oxford 0-15 grading scheme.

During the Site Qualification Visit and the Site Initiation Visit, the site must prove that he has a maintenance certificate for the slit lamp. During the clinical investigation, the monitor should verify that the maintenance is performed (cf. manufacturer guidelines).

During the clinical investigation, the same slit lamp must be used for the same patient at each visit.

6.1.7 Procedures for the Replacement of Patients

The number of screened patients will be followed to obtain 74 randomised patients.

A screen-failed patient (i.e. patient who consent to participate in the clinical investigation and undergo Visit#1 but not subsequently randomised) may be rescreened one time.

Randomised patients who withdraw will not be replaced by another patient. The patient number and associated randomisation number of the withdrawn patient must not be reassigned to a different patient.

6.1.8 Investigation Sites

Patients will be enrolled in approximately 4 investigational sites in EU.

The Sponsor will maintain an updated list of PIs and investigation sites, separately from this CIP, throughout the duration of the clinical investigation. The definitive list will be provided with the CIR.

6.1.9 Definition of Completion of the Clinical Investigation

The clinical investigation completion is defined with the last visit of the last patient.

In the case of early termination of the clinical investigation (see Section **16.2**), the date of the early termination shall be deemed to be the date of the clinical investigation completion.

6.2 IMD(S) AND COMPARATOR(S)

6.2.1 Description of the Exposure to the IMD

IMD will be administered by the patient every day from D1 until Visit 4 (included), one drop in each eye 3 to 6 times daily into the lower conjunctival sac of each eye.

No IMD instillation must be done at least 2 hours before Visit#3 and 4. However, the first instillation can be done any time after the patient has completed the randomisation visit.

There will be two treatment groups:

[figure not shown]
- T2769 (test device)
- Hylo-Forte® (comparative device)

A detailed description of T2769 and of Hylo-Forte® is available in Section **0**.

6.2.2 List of any Other Medical Device or Medication to be Used during the Clinical Investigation

6.2.2.1 Run-in Treatment

Once all screening criteria have been checked, the patient will receive a box containing 1 bottle of Hydrabak® treatment for the run-in period between Day-10/Day-7 to Day 1. The patient will instil 1 drop in each eye 3 to 6 times daily.

6.2.2.2 *Auxiliary Products*

An auxiliary product is defined as a product used for the needs of a clinical investigation as described in the CIP, but not as an IMD.

Fluorescein [REDACTED] a small amount (micro instillation) of fluorescein will be applied in the upper bulbar conjunctiva of each eye by the investigator at visits 2, 3 and 4 to perform the slit lamp examination: TBUT and corneal/conjunctival staining with Oxford 0-15 grading scheme. Conjunctival staining is assessed with a yellow filter.

Yellow filter: it is used for the assessment of the conjunctival staining with fluorescein. The filter is placed between the slit lamp objective and the patient eye to enhance contrast.

Petri dishes and inoculation loops: they are used to perform the fluorescein micro instillation. Some drops of fluorescein are put in a petri dish and a small amount of fluorescein is collected with an inoculation loop.

Schirmer-Plus: while the patient looks upwards, the lower lid will be drawn gently downwards and temporally. The rounded bent end of a sterile Schirmer test strip will be hooked in the lower conjunctival sac over the temporal one-third of the lower eyelid margin. After five minutes, the moistened paper is removed and the length of the tear absorption on the strip will be measured (in millimeters).

Urine pregnancy test: each childbearing potential woman will perform a urine pregnancy test at Visit#1 and Visit#4.

[figure not shown]
6.2.3 Number of IMD to be Used, Together with a Justification

During the clinical investigation, each patient will receive 1 bottle of Hydrabak® and the IMD (4 bottles of T2769 or Hylo-Forte®) to cover run-in and active treatment period.

6.3 PATIENTS

6.3.1 Inclusion Criteria

- *At screening visit*
 - 1.1. Informed consent signed and dated (obtained prior to initiating any procedures).
 - 1.2. Patient aged ≥ 18 years old.
 - 1.3. Persistence of dry eye syndrome, despite artificial tears use in the previous month prior to the screening visit.

[figure not shown]
6.3.2 Exclusion Criteria

[figure not shown]
Patient will NOT be eligible if ONE OR MORE of the following criteria is met at both screening and randomisation visits.

Ophthalmic Exclusion Criteria in AT LEAST ONE EYE [2.1]

- 2.1.1 Far best-corrected visual acuity (BCVA) $\geq +0.7$ LogMar (e.g., ≤ 0.2 in decimal value or $\leq 20/100$ Snellen equivalent or ≤ 50 (ETDRS).

Patient with previous or current ophthalmic condition as defined in the following table:

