6 DESIGN OF THE CLINICAL INVESTIGATION

6.1 GENERAL

6.1.1 Justification of the Investigation Design

Methodology: a 5-week, international, multicentre, randomised, investigator-masked, 2 parallel groups (T2769 versus Hylo-Forte®) investigation.

- Multicentre

The investigation will be performed in different sites in EU.

A multicentre (and multi-investigator) design will provide the possibility of recruiting the patients from a wider population than a single-centre design and of using the device in a broader range of clinical settings, thus presenting an experimental situation that is more typical of future use. In this case, the involvement of a number of investigators also gives the potential for a wider range of clinical judgments concerning the value of the therapeutic intervention. In addition, it is also a practical means of accruing sufficient patients to satisfy the investigation objective.

- Randomised

At the randomisation visit on Day 1, a patient fulfilling all eligible criteria will be randomly assigned to 1 of the 2 treatment groups (T2769 or Hylo-Forte®). Randomisation ensures the investigator remains masked to product assignment for DES treatment. It is generally considered the most reliable method for evaluating the effects of interventions.

- Choice of run-in period

Patients meeting the screening criteria will undergo a 7-10-days run-in period. During this period, all patients will substitute their current dry eye treatment with Hydrabak®, ophthalmic solution containing NaCl 0.9%. Patients will instill 1 drop in each eye, from 3 to 6 times daily.

[Redacted content block] (Baudouin et al. 2017; Chiambretta et al. 2017; Labetoulle et al. 2018; Holland et al. 2019).

- Investigator-masked

A double-masked investigation design is not possible due to different commercial packaging between T2769 – Hylo-Forte®.

However, the identity of the IMD given to each patient will not be known for the masked investigator who is independently in charge of the ophthalmic examination.

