6.1.2 Description of the Measures to be Taken to Minimize or Avoid Bias

6.1.2.1 Randomisation

The use of randomisation attempts to mitigate accidental bias (such as selection bias), promoting comparability of the study groups and serves as a basis for statistical inference for quantitative evaluation of the treatment effect.

The randomisation code list stratified by site and lists of IMDs kit numbers for the packaging is generated by the CRO responsible for biometry. Patients will be randomised on a 1:1 basis to T2769 or Hylo-Forte® respectively.

Randomisation list(s) and lists of IMD numbers for the packaging are to be kept securely by the editor according to their procedures.

The IMD packaging list is to be kept by the company responsible for manufacturing and labelling of the treatment kits.

The randomisation and the IMD kit number will be allocated to the patients according to randomisation list using an Interactive Response Technology (IRT).

Randomisation will occur at Randomisation Visit (Visit #2 - D1) after all procedures have been performed and eligibility for the clinical investigation confirmed. The patient who meets the eligibility criteria will be randomly assigned to treatment and associated to a randomisation number.

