During the whole investigation treatment period, the **masked investigator and/or delegate** will remain masked to the IMD (T2769 – Hylo-Forte®). He/she will not receive the returned IMD from the patients.

All information regarding the use of the IMDs will be contained in the package given to patients.

The IMDs must be dispensed only to patients in accordance with the CIP and the randomisation.

As soon as the patient has signed the Informed Consent, he/she will receive a patient number in the Electronic Case Report Form (e-CRF).

Once all screening criteria have been checked, the patient will receive a box including Run-in Hydrabak® treatment for the run-in period.

At the randomisation visit (Visit #2 - D1), once inclusion and exclusion criteria have been checked and once the patient is eligible, the randomisation will be performed and the IRT will provide the IMD kit number allocated to the patient.

At the other visit (Visit #3 - D15) with dispensation, the IRT will provide the IMD kit number allocated to the patient.

Two dispensations will be performed as follows:

- At randomisation (Visit #2 - D1): one box containing enough bottles for the treatment period Day 1 to Day 15 ± 1 day will be provided by the investigator (or delegate) or pharmacist with the number assigned by the IRT.
- At Visit #3 - D15: one box containing enough bottles for the treatment period Day 15± 1 day to Day 36 ± 3 days will be provided by the investigator (or delegate) or pharmacist with the number assigned by the IRT.

The site team member will instruct patient on the method of instilling the doses and will train his / her patient to not disclose the IMD characteristics neither during the visit nor when reporting / discussing AE / Device Deficiency (DD). If the IMD is dispensed by a masked investigator, he must not open the IMD kit in order to avoid unblinding.

[REDACTED]

6.1.2.6 *Primary Performance Endpoint*

The primary performance endpoint is the change from baseline^a (D1) in total ocular surface staining grade according to Oxford 0-15 grading scheme^b at D36 in the study eye^c.

It is the most commonly used endpoint in clinical trials with DED patients. It is performed to detect ocular damage surface, which is considered as a hallmark sign of DED.

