Cornea and conjunctiva staining is represented by punctate dots on a series of panels (A-E). Staining ranges from 0-5 for each zone and from 0-15 for the total exposed inter-palpebral

conjunctiva and cornea. The dots are ordered on the log scale ([REDACTED] Oxford scale) (see Section 19.5).

The score for each area will be recorded for each eye. The global score (sum of score reported for each area: corneal + conjunctival) will be used for statistical analysis. The statistical analysis will be performed following original oxford scale [REDACTED]

TBUT and ocular surface staining will be assessed after micro instillation of fluorescein. Some drops of fluorescein are put in a petri dish and a small amount of fluorescein is collected with an inoculation loop and then applied to the upper bulbar conjunctiva. This process will be detailed in a specific guide provided to investigation sites.

A slit lamp examination will also be performed at Visit #1 (Screening visit) for evaluation of the prohibited ophthalmic conditions in order to verify the ocular eligibility.

6.4.1.2.6 *Schirmer Test*

The Schirmer test will be performed without anaesthesia (Test I). The test should be done **without touching directly the strip with the finger** to avoid contamination of skin lipids.

The strip should be placed in the temporal part to avoid any contact with the cornea. The patient should keep the eyes closed. Values should be measured just at the end of the 5 minutes.

The Schirmer test will be measured in mm/5 min in each eye and at D1, D15 and D36 visits.

6.4.1.2.7 *Performance Assessment by the investigator*

The investigator must answer to the following question at the end of the patient examination at D15 and D36:

“Do you consider the IMD performance as:

- Very satisfactory
- Satisfactory
- Not very satisfactory
- Unsatisfactory”

6.4.1.2.8 *Global performance by patient*

The global performance is assessed by the patient using a vocal NRS scale. The investigator must ask the following question in local language:

“In a scale from 0 to 10, where 0 is COMPLETELY UNSATISFIED and 10 is COMPLETELY SATISFIED, indicate the number which corresponds the best to your overall satisfaction with the efficacy of the study product in treating your dry eye” (see Section 19.7).

The patient must answer the question verbally.

6.4.1.2.9 *Tear level of inflammatory cytokines (IL-6 and IL-8)*

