A tear sampling of at least 5 µL will be performed at D1, D15 and D36 in the study eye using a method which is defined in a specific guide. The sample will be analysed by central laboratory in order to assess the level of inflammatory cytokines in tears. The Tear sampling will be done after answer to patients’ questionnaires and before ocular examinations.

To prevent the tear sampling from interfering with other ocular assessments, it will be required to wait at least 15 minutes after the sampling is performed to continue with the next ocular assessment.

6.4.1.3 *Safety measures*

6.4.1.3.1 *Adverse Events*

Ocular and systemic AEs will be collected by the investigator (or authorised assessor/delegate) at each visit. In case of appearance of a new clinically significant sign or symptom, it should be reported as an AE. In case of clinically significant worsening of a pre-existing sign or symptom, it should be reported as an AE.

The handling of AEs is detailed in Section 0.

6.4.1.3.2 *Incidents*

Incidents will be collected by the unmasked investigator (or authorised assessor/delegate) at D1, D15 and D36 visits.

6.4.1.3.3 *Ocular Symptoms immediately after drop instillation*

The severity of ocular symptoms immediately after drop instillation will be assessed by the patient.

“Since the last visit, have you felt any unusual ocular sensation immediately after drop instillation(s)?

The following symptoms will be evaluated:

- Burning/Irritation
- Stinging/Eye Pain
- Itching/pruritus
- Eye dryness feeling
- Foreign body sensation
-

Severity will be assessed based on a 4-point scale:

- 0 = Absent,
- 1 = Mild - Present but not disturbing,
- 2 = Moderate - Disturbing
- 3 = Severe - Very disturbing.

The translation of these terms will be provided to the site.

6.4.1.3.4 *Visual Acuity*

Far BCVA will be assessed in each eye at each visit using the same chart (for example a Snellen chart) throughout the clinical investigation. It can be expressed using units as /10, decimal notation, MAR, logMAR, ETDRS or Snellen notation. It will be analysed after conversion in LogMar. (see Section 19.6).

6.4.1.3.5 *Ocular Tolerance Assessment by the investigator*

The investigator must answer to the following question in local language:

“How do you consider the IMD ocular tolerance?

- Very satisfactory
- Satisfactory
- Not very satisfactory
- Unsatisfactory”

6.4.1.3.6 *Ocular Tolerance Assessment by the Patient*

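### Does CIP 6.3.2 let in a patient who meets an exclusion criterion at only one of the two pre-treatment visits?

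*Protocol*

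**What the plan says.** CIP 6.3.2 introduces the exclusion list with "Patient will NOT be eligible if ONE OR MORE of the following criteria is met at both screening and randomisation visits". The first listed criterion, 2.1.1, is a cut-off on far best-corrected visual acuity. A table of past or present eye conditions is announced next, but neither it nor the later criteria appear in the published text.

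Other sections describe how eligibility is decided.

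- **Visit 1.** CIP 6.1.1 states: "Patients meeting the screening criteria will undergo a 7-10-days run-in period". CIP 6.1.5.1 lists verification of the criteria, then a status entry for whether the run-in starts, then dispensing of the run-in product. CIP 6.1.2.5 gives the same order: "Once all screening criteria have been checked, the patient will receive a box including Run-in" product. CIP 6.4.1.2.5 says that the slit lamp examination at this visit is done "for evaluation of the prohibited ophthalmic conditions in order to verify the ocular eligibility".
- **Visit 2.** CIP 6.1.5.2 lists verification of the criteria again, ahead of randomisation, with a status entry of screen failure or randomised. CIP 6.1.2.1 places randomisation "after all procedures have been performed and eligibility for the clinical investigation confirmed". CIP 6.1.2.5 and 6.3.5 say the same in other words.

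On visual acuity, CIP 6.4.1.3.4 states: "Far BCVA will be assessed in each eye at each visit using the same chart".

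**The concern.** The sentence attaches the two visits to the criterion being met, not to the act of checking. On that reading, a patient whose acuity crosses the cut-off at screening but not at randomisation, or the reverse, is not caught. Nor is a patient who develops a listed condition during the 7 to 10 days of run-in. Because the sentence says if and not only if, it does not declare such patients eligible; it leaves them out.

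CIP 6.3.2 is the text against which exclusions are judged. CIP section 10 names departures from the inclusion and exclusion criteria as an example of important deviations for which enrolment at a site could be stopped. It also has all deviations graded minor or major before database lock. SAP 6.2.1 counts patients who met every eligibility criterion. With about four sites, two people could label the same one-visit case differently, and each could point to a sentence in support.

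**Working it through.** No arithmetic applies, and the plan gives no figure to reproduce. The check compares the two readings of 6.3.2 with the visit procedures.

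**Step 1: the four patterns for one criterion.**

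| Met at Visit 1 | Met at Visit 2 | Both visits required | List applied at each visit |
|---|---|---|---|
| No | No | Not excluded | Not excluded |
| Yes | Yes | Excluded | Excluded at Visit 1 |
| Yes | No | Not covered | Excluded at Visit 1 |
| No | Yes | Not covered | Excluded at Visit 2 |

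The readings differ in two of the four rows.

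**Step 2: which reading the procedures can run on.** Suppose a criterion must be present at both visits. At Visit 1 the second result does not yet exist, so no exclusion criterion could stop the run-in, and the Visit 1 check could exclude nobody. Now suppose that Visit 1 does turn away anyone who meets a criterion there. Everyone who reaches Visit 2 then had no criterion at Visit 1, nobody can have one at both visits, and the Visit 2 exclusion check could exclude nobody. Either way, one of the two checks in CIP 6.1.5.1 and 6.1.5.2 is empty. Only the reading that applies the list at each visit gives both checks something to do.

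**Step 3: how far the wording reaches.** Visual acuity is the one visible criterion with a value measured at both visits. For conditions described as past or present, one seen at screening still counts as past at Visit 2, so only onset between the visits is left. The criteria not shown may carry their own timing, as the inclusion criteria in CIP 6.3.1 do.

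**Step 4: what depends on it in the analysis.** The primary analysis uses the full analysis set. CIP 7.1 and SAP section 5 define that set by randomisation, at least one dose, and a baseline and a post-randomisation assessment. Eligibility is not part of that definition, so labelling a one-visit case differently moves nobody in or out of it. The per-protocol set removes patients with major deviations likely to affect the primary outcome seriously. CIP section 10 has exclusions from the analysis sets discussed at a blind data review before lock.

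**The case for a change.** The strongest argument for a correction is that a Visit 1 decision cannot rest on a rule that needs the Visit 2 result, so 6.3.2 and 6.1.5.1 cannot both operate as written. Visual acuity is a real criterion with a numerical cut-off, and it could fall on different sides of that cut-off 7 to 10 days apart. A one-line clarification would cost little.

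The logical point stands, but it counts against the word-for-word reading more than against the plan. It shows that this reading cannot be what was meant, and a workable reading of the same words is available. A sentence that leaves a case out does not contradict sections that cover it.

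The pregnancy test schedule might seem to add support. Tests fall at Visits 1 and 4 only (CIP 6.2.2.2), so a positive test at both screening and randomisation cannot occur. But the excluded state is pregnancy, not a test result, and the text of that criterion is not shown. This adds nothing firm.

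What remains is that the sentence is clumsy and a reader who looks at 6.3.2 alone could misread it.

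**Conclusion.** The wording of 6.3.2 is ambiguous, but no change to the plan follows. A site that works through the Visit 1 and Visit 2 lists already turns away a patient who meets a criterion at either visit, so a corrected sentence would ask for nothing new. A disputed case can be settled at the blind data review that CIP section 10 already provides. A separate amendment would need ethics and authority approval (CIP section 9) and would alter no result.

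In size, the readings part in two of four patterns, one visible criterion is measured at both visits, and the number of patients concerned is not given and cannot be derived. The sample size of 74, the margin of 2 points and the primary model do not depend on the sentence.

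This rests on two assumptions: that sites follow the visit procedures, and that the criteria not shown do not themselves require presence at both visits. The e-CRF and IRT logic is not visible, so how it handles a one-visit case cannot be confirmed from the documents.
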